Title	A Drug Utilisation Study of Domperidone in Europe Using Databases	
Protocol version identifier	Version 2: 20 July 2016	
Date of last version of protocol	Version 1: 3 March 2016	
EU PAS register number	Study not registered, but will be registered upon approval of the protocol	
Active substance	Domperidone	
Medicinal product	Domperidone	
Product reference	ATC code:A03FA03	
Procedure number	EMEA/H/N/PSP/J/0031	
Marketing authorisation holder(s)	Janssen Research & Development on behalf of the Domperidone Collaboration Study Group (a group of all MAHs involved in the Consortium)	
Joint PASS	Yes	
Research question and objectives	s The objective of the study is to investigate the effectiveness of risk minimisation measures and to describe the prescribing patterns before and after the changes to the domperidone label in routine clinical practice in selected European countries regarding the following measures:	
	1. Maximum daily dose (30 mg for adults, 0.25 mg/kg TID for children)	
	2. Concomitant medications that prolong the QT-interval or are potent CYP3A4 inhibitors	
	 Prescribing to patients with contraindicated conditions, e.g., moderate or severe liver disease, underlying cardiac diseases 	
	4. Prescribing for label indication	
	5. Prescribing for off-label indications	
Country (ice) of state	o. Lengui of treatment (greater than / days)	
Country(-ies) of study	France, Germany, United Kingdom, Belgium, and Spain	
Author	The DUS protocol subcommittee of the Domperidone Collaboration Study Group	

A Post-Authorisation Safety Study (PASS) Protocol

Marketing Authorisation Holder(s)

Marketing authorisation holder(s)	Janssen Research & Development on behalf of the	
	Domperidone Collaboration Study Group	
MAH contact person	[name], Global Regulatory Affairs: [contact]	

2. LIST OF ABBREVIATIONS AND DEFINITION OF TERMS

Abbreviations

adverse drug reaction	
Committee for Human Medicinal Products	
Clinical Practice Research Datalink	
Direct Healthcare Professional Communication	
European Medicines Agency	
The electronic ENCePP E-Register of Studies	
(available at: http://www.encepp.eu/encepp/studiesDatabase.jsp)	
Federal Agency for Medicines and Health Products	
Gastro-oesophageal reflux disease	
inflammatory bowel syndrome - also known as inflammatory bowel disease	
Longitudinal Patients Database	
Marketing Authorisation Holder(s)	
numerical daily dose	
Observational Medical Outcomes Partnership Common Data Model	
EU Pharmacovigilance Working Party	
Patient Information Leaflet	
Pharmacovigilance Risk Assessment Committee	
pro re nata (as needed)	
Summary of Product Characteristics	

3. **RESPONSIBLE PARTIES**

The main responsible parties are presented in Table 1.

 Table 1:
 List of All Main Responsible Parties

Responsible Party	Name and Affiliation
Consortium	Domperidone Collaboration Study Group (for full membership, please refer to Annex 1).
Sponsor	Janssen Research & Development on behalf of the Domperidone Collaboration Study Group (a group of all MAHs involved in the Consortium)
Principal / Coordinating Investigator	[name]
	Senior Director, Janssen PRD
	Department of Epidemiology

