4. ABSTRACT

Title of Study

A Drug Utilisation Study of Domperidone in Europe Using Databases

Rationale and Background

In March 2013, the European Medicines Agency (EMA) Pharmacovigilance Risk Assessment Committee (PRAC) initiated a review of domperidone-containing medicines at the request of the Federal Agency for Medicines and Health Products (FAMHP), under Article 31 of Directive 2001/83/EC over concerns about cardiac adverse effects of domperidone. Subsequently, PRAC recommended that the product label (Summary of Product Characteristics/SmPC and Patient Information Leaflet/PIL) of domperidone-containing medicines be updated to strengthen the information regarding cardiac risks. In addition, PRAC raised concerns that there may be off-label use of domperidone for the stimulation of lactation in breastfeeding women, for the treatment of gastro-oesophageal reflux disease (GERD), for the treatment of diabetic and non-diabetic gastroparesis, and for the treatment of symptoms of postural hypotension in Parkinson's patients. More recently the EMA asked that inflammatory bowel syndrome (IBS) be included in the present study as an off-label indication.

The recommended changes following conclusion of the Article 31 referral included the following:

- restriction of the indication to nausea and vomiting;
- limitation of duration of use to 7 days;
- reduction of the maximum daily dose to 10 mg TID for adults and adolescents (12 years of age and older and weighing 35 kg or more);
- reduction of the maximum daily dose to 0.25 mg/kg TID for neonates, infants, children (less than 12 years of age), and adolescents weighing less than 35 kg;
- contraindication of the combination with other drugs that increase the cardiac risks by themselves or increase the plasma level of domperidone; and
- contraindication in patients with moderate or severe hepatic impairment or certain cardiac conditions.

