7.2. Background

In 2011, the EU Pharmacovigilance Working Party (PhVWP) recommended that the product information for domperidone-containing medicines should be updated to reflect the risk of adverse cardiac effects of domperidone including QT prolongation, arrhythmias, and sudden cardiac death, and that domperidone should be used with caution in patients with certain heart conditions, including heart failure, a previous heart attack, angina (chest pains), and heart rhythm disorders. In response to this recommendation, the SmPC was updated in 2012 to include QT prolongation as an adverse drug reaction (ADR).

In March 2013, the EMA PRAC initiated a review of domperidone-containing medicines at the request of the Federal Agency for Medicines and Health Products (FAMHP), under Article 31 of Directive 2001/83/EC over concerns about cardiac adverse effects of domperidone. Subsequently, PRAC recommended that the product label (Summary of Product Characteristics/SmPC and Patient Information Leaflet/PIL) of domperidone-containing medicines should be updated to strengthen the information regarding cardiac risks. In addition, PRAC raised concerns that there may be off-label use of domperidone for the stimulation of lactation in breastfeeding women, for the treatment of

gastro-oesophageal reflux disease (GERD), for the treatment of diabetic and non-diabetic gastroparesis, and for the treatment of symptoms of postural hypotension in Parkinson's patients. More recently the EMA asked that IBS be included in the present study as an off-label indication.

The recommended changes following conclusion of the Article 31 referral included the following:

- restriction of the indication to nausea and vomiting;
- limitation of duration of use to 7 days;
- reduction of the maximum daily dose to 10 mg TID for adults and adolescents (12 years of age and older and weighing 35 kg or more);
- reduction of the maximum daily dose to 0.25 mg/kg TID for neonates, infants, children (less than 12 years of age), and adolescents weighing less than 35 kg;
- contraindication of the combination with other drugs that increase the cardiac risks by themselves or increase the plasma level of domperidone; and
- contraindication in patients with moderate or severe hepatic impairment or certain cardiac conditions.

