9.3.2. Indication

Indication will be estimated from the diagnoses recorded in the time period preceding each domperidone prescription:

- The indication for the prescription will be defined as nausea/vomiting if the subject has a recorded diagnosis classified as nausea or as vomiting, on the day of the prescription or in the preceding 7 days.
- For those prescriptions whose indication is not defined as nausea/vomiting, the indication will be defined as off-label if the subject has, in the 2 months up to and

including the date of domperidone prescription, a diagnosis classified as one of the following:

- o GERD;
- Abdominal bloating, gastric dysmotility, delayed gastric emptying;
- o IBS;
- Suppressed lactation, failed lactation, lactation not established, decreased lactation, lactation problem; or
- Orthostatic hypotension and a diagnosis of Parkinson's disease.
- For those prescriptions not classified as above, the indication will be classified as unknown.

For a list of the diagnostic terms and codes that will be used to identify the above conditions, see Annex 6.

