ANNEX 6: VARIABLES TO BE USED IN DATABASES

Condition	ICD-9 Codes	Text
Abdominal Bloating	536.3	Gastroparesis
GERD	530.11	Reflux esophagitis
GERD	787.1	Heartburn
GERD	787.2	Dysphagia
GERD	787.20	Dysphagia, unspecified
GERD	787.21	Dysphagia, oral phase
GERD	787.22	Dysphagia, oropharyngeal phase
GERD	787.23	Dysphagia, pharyngeal phase
GERD	787.24	Dysphagia, pharyngoesophageal phase
GERD	787.29	Other dysphagia
IBS	555	Regional enteritis
IBS	555.0	Regional enteritis of small intestine
IBS	555.1	Regional enteritis of large intestine
IBS	555.2	Regional enteritis of small intestine with large intestine
IBS	555.9	Regional enteritis of unspecified site
IBS	556	Ulcerative colitis
IBS	556.1	Ulcerative (chronic) ileocolitis
IBS	556.3	Ulcerative (chronic) proctosigmoiditis
IBS	556.5	Left-sided ulcerative (chronic) colitis
IBS	556.6	Universal ulcerative (chronic) colitis
IBS	556.8	Other ulcerative colitis
IBS	556.9	Ulcerative colitis, unspecified
Nausea and Vomiting	78.82	Epidemic vomiting syndrome
Nausea and Vomiting	536.2	Persistent vomiting
Nausea and Vomiting	564.3	Vomiting following gastrointestinal surgery
Nausea and Vomiting	643	Excessive vomiting in pregnancy

Condition	ICD-9 Codes	Text
Nausea and Vomiting	643.2	Late vomiting of pregnancy, unspecified as to episode of care or not applicable
Nausea and Vomiting	643.2	Late vomiting of pregnancy
Nausea and Vomiting	643.21	Late vomiting of pregnancy, delivered, with or without mention of antepartum condition
Nausea and Vomiting	643.23	Late vomiting of pregnancy, antepartum condition or complication
Nausea and Vomiting	643.8	Other vomiting complicating pregnancy
Nausea and Vomiting	643.8	Other vomiting complicating pregnancy, unspecified as to episode of care or not applicable
Nausea and Vomiting	643.81	Other vomiting complicating pregnancy, delivered, with or without mention of antepartum condition
Nausea and Vomiting	643.83	Other vomiting complicating pregnancy, antepartum condition or complication
Nausea and Vomiting	643.9	Unspecified vomiting of pregnancy
Nausea and Vomiting	643.9	Unspecified vomiting of pregnancy, unspecified as to episode of care or not applicable
Nausea and Vomiting	643.91	Unspecified vomiting of pregnancy, delivered, with or without mention of antepartum condition
Nausea and Vomiting	643.93	Unspecified vomiting of pregnancy, antepartum condition or complication
Nausea and Vomiting	787.03	Vomiting alone
Nausea and Vomiting	787.0	Nausea and vomiting

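### IBS is expanded as a hybrid term and coded in Annex 6 only as inflammatory bowel disease, so a recorded irritable bowel diagnosis falls into the unknown indication class

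*Protocol*

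**What the plan says.** The abbreviation list in Protocol Section 2 glosses the term as "inflammatory bowel syndrome - also known as inflammatory bowel disease". The Abstract gives the same expansion and explains why the condition is in the study: "More recently the EMA asked that inflammatory bowel syndrome (IBS) be included in the present study as an off-label indication". Section 7.2 repeats the request with the abbreviation alone. The same section gives the relevant label change as "restriction of the indication to nausea and vomiting".

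Section 9.3.2 assigns an indication to each prescription in three steps. A nausea or vomiting diagnosis on the day or in the 7 days before comes first. Failing that, a diagnosis from a short list of off-label conditions, IBS among them, in the 2 months up to the prescription makes it off-label. Otherwise: "For those prescriptions not classified as above, the indication will be classified as unknown". The codes come from the annex: "For a list of the diagnostic terms and codes that will be used to identify the above conditions, see Annex 6".

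The IBS rows of Annex 6 have entries such as "Regional enteritis of small intestine with large intestine" and "Universal ulcerative (chronic) colitis". Section 9.7 then builds four versions of the composite. Versions 1 and 3 treat an unknown indication as nausea and vomiting; versions 2 and 4 treat it as off-label.

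**The concern.** The term joins the word syndrome and the initials IBS, which most clinical readers take to mean irritable bowel syndrome, to inflammatory bowel disease, which is a different condition. The code list settles the ambiguity in one direction, and nothing in the protocol suggests that the ambiguity was noticed.

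Two things are at stake. First, the row exists because the regulator asked for it. If irritable bowel syndrome was meant, the study as coded does not report it. If inflammatory bowel disease was meant, a table row labelled IBS will be misread. Second, on the protocol's own account the label covers nausea and vomiting only. A prescription whose only recent relevant diagnosis is irritable bowel syndrome therefore has a recorded diagnosis outside the label, yet it is filed with prescriptions for which nothing relevant was recorded.

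**Working it through.** There is no stated figure to reproduce. The check is a trace through the definitions, followed by an illustration of size.

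**Code count (Annex 6, rows labelled IBS)**
- Regional enteritis: 555, 555.0, 555.1, 555.2, 555.9, which is 5 rows.
- Ulcerative colitis: 556, 556.1, 556.3, 556.5, 556.6, 556.8, 556.9, which is 7 rows.
- Total 5 + 7 = 12. No row anywhere in the annex names irritable bowel syndrome.

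**Path of one prescription.** Take a patient with an irritable bowel diagnosis in the last 2 months, no nausea or vomiting code in the last 7 days, and no other listed off-label diagnosis in the last 2 months.
- Section 9.3.2, step 1: not nausea or vomiting.
- Step 2: not off-label, because no listed code matches.
- Step 3: unknown.
- Section 9.7: passes the indication component in versions 1 and 3 and fails it in versions 2 and 4, so 2 of 4 versions accept it.
- Indication tabulation (Section 9.7) and time trend of apparent indication (Section 8.2): shown as unknown, whichever version of the composite is used.

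Passing the indication component does not make the prescription compliant. It must also meet the dose, contraindication and co-medication conditions and, in version 3, have no more than 7 days' supply. If s is the share of prescriptions on this path and f the fraction of them that meet the remaining conditions, compliance is overstated by m = s × f, which is at most s.

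**Effect on the risk ratio.** With p the true compliance in each period, and the ratio taken as post over pre as in Section 9.5:

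observed RR = (p_post + m_post) / (p_pre + m_pre)

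All values of m are assumptions, as are the true RR of 1.20 and the baseline. At p_pre = 0.50, p_post = 0.60:
- m = 1% in both periods: 0.61 / 0.51 = 1.196
- m = 5% in both periods: 0.65 / 0.55 = 1.182
- m falling from 5% to 2%: 0.62 / 0.55 = 1.127
- m falling from 5% to 0%: 0.60 / 0.55 = 1.091

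Other baselines, same true RR:
- 30% (p_post = 0.36): 1.194 for a constant 1%, 1.171 for a constant 5%, 1.086 for 5% falling to 2%.
- 70% (p_post = 0.84): 1.197, 1.187 and 1.147 respectively.

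A stable share pulls the ratio slightly towards 1. A share that shrinks because prescribers respond to the new label removes real improvement from versions 1 and 3.

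**The case against.** The strongest reply is that the protocol is consistent. It spells the condition out, equates it with inflammatory bowel disease, and codes that disease. This stands: a reader might infer an internal contradiction or a coding slip, and the text shows neither. A reader might also infer that the study fails the regulator's request. That would need the request itself, which the protocol does not reproduce.

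A second reply is that every unlisted diagnosis ends up as unknown, so irritable bowel syndrome deserves no special treatment. This would be decisive for an arbitrary diagnosis. It is weaker here, because this one shares its abbreviation with a condition that the regulator named.

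Third, the design already brackets unknown indications: Section 9.3.6 names them as an area of uncertainty, the composite is run both ways, and Section 8.1 promises a risk ratio and confidence interval for each version. This largely stands for the composite. It does not help the indication table or the time trend. Section 9.9.2 ties the uncertainty to prescriptions without a plausible recorded diagnosis, whereas here a diagnosis is on file.

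Fourth, a diagnosis within 2 months does not prove the reason for prescribing, as Section 9.9.2 acknowledges. That is correct, but the same inference is accepted for every off-label condition on the list.

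Finally, Annex 6 as shown gives ICD-9 codes only, and Annex 5 assigns ICD-9-CM to Spain alone. How IBS will be coded in ICD-10 (France, Germany, Belgium) and Read (United Kingdom) is inferred from the definition. This limits the claim about codes, but it makes a clear definition more important, because those lists have to be built from it.

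**Conclusion.** The point holds as a defect of definition and classification, worth correcting before extraction. The term is ambiguous, the ICD-9 list resolves it to inflammatory bowel disease only, and a recorded irritable bowel diagnosis with no other listed code is reported as unknown and accepted on indication in versions 1 and 3.

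The size cannot be taken from the protocol. It would be tempting to say that compliance in those versions is overstated by the whole share of irritable bowel prescriptions, but that share is only a ceiling, since the other composite conditions must also be met. On the assumed constant 1% to 5% wrongly counted as compliant, the risk ratio barely moves (1.20 to between 1.196 and 1.182 at 50% baseline). The larger shifts need the further assumption that the share falls after the label change. Versions 2 and 4 are not affected in this way.

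**What to change.** Check the regulator's request to confirm which condition was meant, and correct the term in the abbreviation list and the Abstract. Whatever the answer, add irritable bowel syndrome as its own off-label entry in Section 9.3.2 and as its own rows in Annex 6, with matching ICD-10 and Read codes. Keep the present codes under the name inflammatory bowel disease, and report the two conditions separately in the indication table and time trend.

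The diagnoses are already in the databases, so the cost is a few codes and one extra table row. The downside is a slightly lower on-label rate in versions 1 and 3.

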4. ABSTRACT

Title of Study

A Drug Utilisation Study of Domperidone in Europe Using Databases

Rationale and Background

In March 2013, the European Medicines Agency (EMA) Pharmacovigilance Risk Assessment Committee (PRAC) initiated a review of domperidone-containing medicines at the request of the Federal Agency for Medicines and Health Products (FAMHP), under Article 31 of Directive 2001/83/EC over concerns about cardiac adverse effects of domperidone. Subsequently, PRAC recommended that the product label (Summary of Product Characteristics/SmPC and Patient Information Leaflet/PIL) of domperidone-containing medicines be updated to strengthen the information regarding cardiac risks. In addition, PRAC raised concerns that there may be off-label use of domperidone for the stimulation of lactation in breastfeeding women, for the treatment of gastro-oesophageal reflux disease (GERD), for the treatment of diabetic and non-diabetic gastroparesis, and for the treatment of symptoms of postural hypotension in Parkinson's patients. More recently the EMA asked that inflammatory bowel syndrome (IBS) be included in the present study as an off-label indication.

The recommended changes following conclusion of the Article 31 referral included the following:

- restriction of the indication to nausea and vomiting;
- limitation of duration of use to 7 days;
- reduction of the maximum daily dose to 10 mg TID for adults and adolescents (12 years of age and older and weighing 35 kg or more);
- reduction of the maximum daily dose to 0.25 mg/kg TID for neonates, infants, children (less than 12 years of age), and adolescents weighing less than 35 kg;
- contraindication of the combination with other drugs that increase the cardiac risks by themselves or increase the plasma level of domperidone; and
- contraindication in patients with moderate or severe hepatic impairment or certain cardiac conditions.

Within the context of risk minimisation measures, PRAC requested that domperidone MAHs perform a drug utilisation study to assess the effectiveness of the above mentioned risk minimisation measures and to monitor the off-label use of the drug. In addition to a physician survey proposed by the MAHs to assess the prescribers' knowledge of the new label of domperidone, EMA suggested the use of a healthcare database as an additional data source to measure domperidone utilisation patterns. This protocol describes a drug utilisation study using healthcare databases in 5 European Union countries.

Research Questions and Objectives

The objective of the study is to investigate the effectiveness of risk minimisation measures and describe prescribing patterns of domperidone, including those pertaining to the off-label use of domperidone, in routine clinical practice in 5 European Union countries.

Primary Objectives: To describe the prescribing patterns before and after the changes to the domperidone label and estimate and compare the overall proportion of domperidone prescriptions before and after implementation of the risk minimisation measures regarding the following measures:

- Composite endpoint consisting of the following components:
 - Maximum daily dose;
 - Duration of use (>7 days)
 - Concomitant medications that prolong the QT-interval or are potent CYP3A4 inhibitors;
 - Prescribing to patients with contraindicated conditions, e.g., moderate or severe liver disease, underlying cardiac diseases; and
 - Prescribing for off-label indications

Secondary Objectives: To estimate the overall proportion of domperidone prescriptions before and after implementation of the risk minimisation measures for domperidone for each of the components of the composite endpoint individually, the time trend of apparent indication, and days supplied (\leq 7 days vs. >7 days), and the age and sex of the people receiving prescriptions.

Study Design

This is a post-authorisation, retrospective, observational cohort study using a pre- and post-design to examine the changes in the prescribing patterns. A cohort of patients initiating domperidone will be identified from existing secondary data sources (IMS, CPRD) in selected European Union countries (France, Germany, United Kingdom, Belgium, and Spain). These countries are selected to provide a range of domperidone usage (from France, which has the highest per capita domperidone use in the EU, to Germany, which ranks number 12 in the EU for per capita domperidone use), and based on the availability of robust longitudinal electronic medical records databases. These data sources will include person-level information on demographics, prescriptions, and diagnoses.

Population

Defined as all patients receiving domperidone in the outpatient setting during the pre-defined periods (pre- and post- implementation periods of the risk minimisation activity) in the selected European Union countries (France, Germany, United Kingdom, Belgium, and Spain). Patients will be included in the study cohort if they have at least 1 prescription for domperidone in the selected databases during the pre-defined periods, and have been registered with the practice and have available medical history for at least 180 days.

Variables

Demographic characteristics (including age, sex, and geographic region); indication; dose per day; use in patients with contraindicated conditions; concurrent use with drug that prolong the QT interval or are potent or strong CYP3A inhibitors, and length of treatment will be examined.

Data Sources

Subject to change based on data availability, patient information on domperidone exposure and study endpoints will be obtained from Longitudinal Electronic Medical Records (EMR) databases, including IMS® Disease Analyzer and CPRD. These are described in Annex 5.

Study Size

The study size will vary according to country and data source. All patients available in the study population will be considered for the analysis. Preliminary estimates indicate that the suggested databases capture at least several thousands of domperidone prescriptions in each of the countries being studied.

Data Analysis

Data analysis in the study will be descriptive. Continuous variables will be presented using appropriate descriptive statistics, such as mean, median, standard deviation and range. Categorical variables will be presented using percent and frequency tables. The rates and 95% CI of all study endpoints (i.e., risk minimisation indicators) will be calculated for the 2011-2015 period, using quarterly time blocks for the pre- and post- risk minimisation implementation periods. The rates will be calculated per 1000 domperidone-treated patients or as percentage of domperidone prescriptions, as appropriate. Paediatric data will be described separately from adult patients and rate of paediatric use will be calculated as fraction of overall domperidone utilisation. All data analysis will be done in SAS using the version that is current when the analyses are done.

The rates for the primary endpoints of the study as the proportion of all prescriptions that are consistent with the revised label will be calculated:

- 1. Prescription for nausea and vomiting, or unknown indication but no recent diagnosis of GERD, gastroparesis, inflammatory bowel syndrome (IBS), symptoms of postural hypotension in Parkinson patients or as an aid to lactation;
- 2. Dose no higher than recommended;
- 3. No prescription to patients with certain cardiac and hepatic conditions; and
- 4. No co-prescription with CYP3A4 inhibitors or QT-prolonging drugs.

Note that additional analyses described in Section 9.3 will address the possibility that an unknown indication may be off-label, and the possibility that domperidone may be used for the entire number of days supplied.

Rates of the study endpoints will be assessed for the 1-year pre-implementation period (1 April 2013 through 31 March 2014) and will be compared with the 1-year post-implementation period (1 October 2014 through 30 September 2015). In addition, each of the above label requirements that contribute to the primary endpoint will be compared for the same two 1-year periods.

In addition:

- 1. The apparent indications, and the days supplied $(\leq 7 \text{ days vs.} > 7 \text{ days})$ will be tabulated.
- 2. There will be a table showing the demographic characteristics, of the study population (sex, age group).

Milestones

Milestones	Planned Date		
Start of data collection	Two months after protocol approval		
End of data collection	When data through SEP2015 become available for analysis (estimated as 4Q2016)		
<registration eu="" in="" pas="" register="" the=""></registration>	Before the start of the study		
Final report of study results*	Twelve months after the end of data collection		
*Timing of final report includes the following:			
Data analysis: Three months after data are available			
Final tables available: Two months after data analysis is complete			
Report writing: Three months			
Report review (full Consortium): Four months			

